While explaining the study, potential subjects will be assured that they will receive all of the medication for their acute headache that they would otherwise receive. Once consented, subjects will be randomized to PMR therapy or MUC. Participants will be told that either group is being tested as an enhancement to the care they typically get in the ED for headache. At the end, they will be told that they will be informed which group they were in. The RV or RA will then collect subjects' health histories (biologic variables) and baseline data in REDCap on an iPad, download the app onto subjects' smartphones, and conduct the sessions (see below). There will be fidelity monitoring.

We will be requesting the Epic Research Team for a report of the following data for patients who visited the ED for headache from 10/22/2017 to 02/18/2019:

- gender
- race
- pcp or neurology care provider
- zip codes - or region they live in
- did they have a neurologist before visiting ED
- did they have diagnosis of migraine prior to visiting the ED
- had they seen a neurologist prior to visiting the ED
- did they attend a follow up appointment
- did they have a Rx for triptans prior to visiting the ED
- did they have a Rx for opioids prior to visiting the ED

PMR: The RV or RA will explain the rationale for PMR and the APP will be uploaded onto the subjects' smartphones. The subject will perform PMR in the ED and discuss the optimal time and place to practice PMR at home.

Subjects will also enter their headache log daily on the APP. The APP will track the amount of time playing the PMR. Subjects will be asked to do the following:

Intervention:

Week 1: 5 min deep breathing at least 5/7 days of the week

Week 2: 5 min PMR session at least 5/7 days of the week

Week 3: 15 min pmr preferred at least 5/7 days of the week

Week 4: pmr at least 4 days a week (optional body scan)

Week 5: pmr at least 3 days a week (optional body scan)

Weeks 6-8: use when it is most helpful (falling asleep, HA coming on, stress)

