The study intervention will be 8 weeks in duration but the full study length will be 6 months. There will be a baseline assessment (T0), a f/u call or email at one week (T1), a 30 day phone call or email assessment (T2), a 60 day phone call/email (T3), and a 90 day phone call/email (T4) (to examine persistence of effect after a month). The last follow-up will be at 6 months to examine persistence of effect 4 months after the intervention ends. As we learned previously, we are adding the option for email as some subjects prefer email.

MUC: To match the time spent with the designated study team member, subjects will be given a general education session consisting of basic migraine information, such as evidence-based ways to treat headaches: treat early, limit acute medications < 2–3 days/week, and call the primary care physician (PCP) if abortive medications are used more frequently. They will be shown a website:

<https://[name].wixsite.com/relaxahead> (to be renamed) The study team member will load the app onto the subject's smartphone but the PMR component will be blocked on the version of the app that the MUC subject receives.

Discharge Plans and Post-Discharge Plans for All Subjects: All subjects will receive written educational material about migraine. This is the standard information about migraine that is printed from Epic when patients are discharged from the ED with migraine. Subjects will be asked to follow-up with a PCP upon discharge from the ED and will be offered an appointment for this follow-up visit unless they have an appointment scheduled. Subjects without a PCP will be referred to a PCP. There will be emphasis on ensuring that the subjects understand the discharge information, which will include the diagnosis and both verbal and written instructions. Letters will be sent to PCPs informing them of the study and stating that they are to treat the subjects as they see fit.

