All subjects will receive follow-up phone calls or emails (from REDCap or send safe emails) at 7 days and 1, 2, 3, and 6 months after discharge. Follow-up will be assured by testing the subject's phone number in front of the subject and asking for alternative contact information. Prior studies have shown that data can be successfully obtained from subjects at 24 hours, and 1 and 3 months-post ED discharge (over 90% follow-up rates). During the calls, the RV or RA will reiterate the importance of adherence with the APP. During the 1, 2, 3 and 6 month calls or emails (from REDCap or send safe emails), they will be asked to complete the REDCap follow-up questionnaires (already part of the IRB submission with the added modification of the MSQv2). They may also receive phone calls or SendSafe emails or texts up to every 3 days if the smartphone app data indicates that they are not completing the headache diary. If benefits do not persist, future studies may add additional interventions. Throughout the study, subjects will be asked to record electronically any new and/or discontinued medications and interactions with the medical community.

The choice of calls, texts or emails came from prior subjects who participated in IRB approved study focus groups. The study team has permission from MCIT to send the following text messages (and an emailing indicating such approval is part of the submission process):

1. Please remember to use the app.
2. Hi, The RELAXaHEAD team is trying to reach you. Please call xxx-yyy-zzz [study phone number]?
3. You are due for your follow-up call/email. Please be sure to call us at xx-yyy-zzzz or respond to the email. - The RELAXaHEAD team.
4. Remember-relaxation is beneficial for your health.
5. The best way to add relaxation into your routine is to pair it with an activity you do each day. Let us know if you want to discuss how to improve your adherence with the RELAXaHEAD app.
6. Research has suggested that the more one is able to practice relaxation, the better one's health. Log into the RELAXaHEAD app when able.

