All subjects will be given a \$60 gift card incentive for participating, and will receive an additional \$1 per day they do the intervention to compensate them for study-related time and data usage costs. If they complete the intervention more than 80% of the total 60 days of the study, then the daily compensation will be doubled. In addition, they will receive \$15 gift cards for the one month and two month f/u emails/calls and \$25 gift cards for the 3 month and 6 month f/u email or phone assessments. Thus, based on the prior adherence data, the max total projected amount that participants will receive is \$200 but if they get the bonus, they could get up to \$260.

This payment is on par with other migraine smartphone studies throughout the country.

Fidelity monitoring will be conducted as in Aim 1.

Data Analysis and Data Monitoring Analysis Plan

Sample Size: The sample size was calculated for the primary outcome (Δ MIDAS) and the secondary outcome (number of headaches/30 days). A study of medication plus behavioral therapy for migraine as compared with medication alone in the outpatient setting showed that the distribution of MIDAS at baseline or 3 months was right-skewed, but the Δ MIDAS was symmetric and approximately normally distributed. Considering Δ MIDAS as the primary outcome can reduce data skewedness and improve study power. Based on the study, the standard deviation (SD) of Δ MIDAS ranges from 5 to 7. With the conservative estimate of SD=7, group sample sizes of 31 and 31 achieve 80% power to detect a clinically significant difference of 5 between the groups, assuming

group standard deviations of 5 and a significance level of 0.05 using a two-sided two-sample t-test. The emergency medicine studies had over 90% follow-up at 3 months and the electronic headache diary studies' follow-up was between 76%–80%. To accommodate potential dropout rate as high as 30%, a total of 90 subjects will be recruited.

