For the secondary outcome of number of headaches in 30 days, group sample sizes of 31 and 31 achieve 80% power to detect a difference of 1.42 assuming an SD of 2 in both groups with a significance level of 0.05 using a two-sided two-sample t-test. Potential non-normal distributions will be considered for the count data of the number of headaches and analyzed using nonparametric tests. A simulation-based sample size calculation was performed assuming Poisson distributions. The sample size of 31 per group has >80% power to detect the difference of 1.4 using a two-sided Mann-Whitney test at significance level 0.05 assuming a Poisson distribution with mean 2 in the control group.

Aim 2 Data Collection and analyses:

PHI will be maintained in a separate log maintained securely as described below under data security.

Symptoms Diary

On the smartphone application platform developed by IRODY (used by the NYUMC epilepsy group for ongoing IRB approved studies), subjects will be trained to keep records of headache occurrence, side effects, compliance and medicine changes on their mobile device. If a subject fails to consistently record their data, they will receive a call/text/email from the RV or RA to ensure compliance with data maintenance. Information prompted by the device will include:

1. Headaches (number, type, and dates)
2. Abortive and preventive migraine drug treatment
3. Concomitant medications
4. Episodes of non-compliance
5. Changes made to migraine medication treatment plan, if any, and reasons for the change
6. Adverse effects, including severity, seriousness, unexpectedness as part of pharmacovigilance
7. Mood and anxiety levels, stress and sleep
8. Healthcare utilization

The symptoms diary may be accessed via the mobile application only. The app also includes the following questionnaires: PROMIS for depression and anxiety, the Perceived Stress Scale, and the Insomnia Sleep Index.

The study team will not share the symptoms diary information with the subject's treating physician. However, subjects can elect to share their data with their treating physician independently.

In addition to the application, REDCap, a HIPAA Compliant research database system, generated emails, and telephone calls by the blinded RAs with data entered into REDCap will be used to collect the MSQv2 and the MIDAS. The PHI of the subjects will only be stored in REDCap. IRODY does not receive PHI in the app or log in process.

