Quality Control: The Clinical Data Monitor will download the data from the Diary Cloud Server. From this download, standard reports including missing days or entries as well as identification of any safety concerns will be created from the downloaded database and examined and reviewed by the Clinical Data Monitor.

Measurements: Our primary outcome, the Migraine Quality of Life (MSQv2) is a validated quality of life measure. In addition, we will check the Migraine Disability Assessment Scale (MIDAS), measures disability over the past 3 months. MIDAS scores were shown to have excellent test-retest reliability, high internal consistency and high external validity using a variety of measures including diary based measures. MIDAS scores are also associated with physician judgements about the severity of headache and the need for treatment. A decrease of 3 points in the MIDAS score corresponds to a one day reduction in headache related disability per month, a clinically meaningful difference. In the Headache Management Trial, persons with headache were randomized to coordinated, guideline-based care vs. usual care. The study was designed to detect a 5-point difference in MIDAS decline between treatment arms and found a highly clinically significant 7 point decline. We will examine the change in disability scores (Δ MIDAS) defined as the difference between MIDAS scores at 3 months and at baseline.

Data Storage and Confidentiality

Each subject will be assigned a unique alphanumeric identifier for use with the app. No PHI is being given to IRODY. The alphanumeric identifiers will be unrelated to the identity of the study subjects. All clinical data/information will be entered into the RedCap database. Only the PI and the RVs/RAs will have access to the linking database.

The consent forms will be kept in a separate locked file cabinet in the Tisch ED. They will be transferred periodically to a locked cabinet at [name]. If someone were to gain illegal access to the locked filing cabinet with study data, they would have no way to link this data to any identifying information.

The research team will perform all data analyses. Data will be stored electronically in a secure research database and will be available for the research team.

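### The app diary is the only adverse-effect source the documents describe; no follow-up contact is stated to ask about harm or why use stopped

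*Combined protocol and SAP*

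**What the plan says.** The Symptoms Diary section lists what the app prompts for. Item 6 is "Adverse effects, including severity, seriousness, unexpectedness as part of pharmacovigilance". The same section adds: "The symptoms diary may be accessed via the mobile application only". Under Quality Control, the Clinical Data Monitor downloads the diary, and "standard reports including missing days or entries as well as identification of any safety concerns will be created from the downloaded database".

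Methods & Procedures gives all subjects contacts at 7 days and at 1, 2, 3 and 6 months; the first two are set out as "a f/u call or email at one week (T1), a 30 day phone call or email assessment (T2". On content it says: "During the calls, the RV or RA will reiterate the importance of adherence with the APP". From month 1 onward the contacts also carry REDCap follow-up questionnaires, whose items are not listed. Subjects whose diary lapses may be contacted as often as every 3 days, and the Symptoms Diary section gives the purpose as keeping the record complete. Six text messages are scripted; calls and emails are not.

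The Risk section foresees two reactions to PMR, pain at the site of an old injury and intrusive memories, and lets subjects stop the exercise. It does not say that the reason for stopping is asked or recorded. The Data Safety Monitoring Plan gives a 24- to 48-hour target for reporting unanticipated events.

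**The concern.** Collection of harm data depends on continued use of the app that delivers the treatment. A subject who reacts badly to PMR and then leaves the app also leaves the only described place for recording the reaction. Missing harm data would then be informative: absence of an entry could mean no harm, or harm followed by stopping. In a trial of 90 subjects, a few unrecorded events could decide whether any PMR harm is seen at all. Reasons for stopping also matter in a pilot, because they separate intolerance from lack of interest.

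**Working it through.** The plan states no figure on this point, so there is none to reproduce. The check compares the routes by which harm could be found, then the calendar, then gives an illustration on assumed values.

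**Routes described**

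| Route | Who | Stated purpose | Adverse-effect question described? |
|---|---|---|---|
| App symptoms diary | All subjects, while they use the app | Headaches, drugs, adverse effects, mood and other items | Yes, item 6 |
| Day 7 contact | All | App adherence | No |
| Month 1, 2, 3 and 6 contacts | All | App adherence; REDCap questionnaires | Not stated; items not listed |
| Non-completion contacts | Subjects with missing entries (optional) | Restore diary entry | No; none of the six texts asks about harm or why use stopped |
| Clinical Data Monitor reports | Built from the diary download | Missing entries and safety concerns | Adds no new source |
| Data Safety Monitoring Plan | Unanticipated events | Time limit for reporting | Gives no way of finding events |

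Subjects are also asked to record medication changes and dealings with medical services electronically. That could show that care was sought, but not a reaction that led only to stopping.

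**Calendar**

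The home programme begins with "Week 1: 5 min deep breathing at least 5/7 days of the week", followed by "Week 2: 5 min PMR session at least 5/7 days of the week". Taking week 1 as days 1–7, home PMR can start on day 8.

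- Scheduled contacts fall on days 7, 30, 60, 90 and about 180. Four of the five come after day 8.
- From day 8 to the day-30 contact is 30 − 8 = 22 days.
- At one contact every 3 days, 22/3 = 7.3, so up to 7 non-completion contacts could fall in that interval.
- PMR is first performed at enrollment, so the day-7 contact follows one exposure.

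Opportunities to ask therefore exist. What is missing is a stated question.

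**Illustration (all rates assumed)**

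Let n = 45 PMR subjects (90/2, equal allocation assumed), p = share harmed, s = share of those harmed who leave the app before entering the harm, and q = share of these harms that contacts find. Harms in subjects who stay in the app are taken as recorded.

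Recorded rate: r = p × (1 − s + s × q). Chance of recording at least one harm: 1 − (1 − r)^45.

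Example with p = 0.05 and s = 0.5. Expected harmed: 45 × 0.05 = 2.25.

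- q = 0: r = 0.05 × 0.5 = 0.025; expected recorded 45 × 0.025 = 1.125; chance 1 − 0.975^45 = 68%.
- q = 0.9: r = 0.05 × 0.95 = 0.0475; chance 1 − 0.9525^45 = 89%.

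| p | All harms recorded | q = 0; s = 25% / 50% / 75% | q = 0.9; s = 25% / 50% / 75% |
|---|---|---|---|
| 2% | 60% | 49% / 36% / 20% | 59% / 58% / 57% |
| 5% | 90% | 82% / 68% / 43% | 89% / 89% / 88% |
| 10% | 99% | 97% / 90% / 68% | 99% / 99% / 99% |

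The loss depends mainly on whether the contacts ask.

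**The case against.** The strongest reply is that the full set of study documents may already cover this. The text is an addendum to a main protocol that is not supplied, and the REDCap questionnaires were submitted separately. Calls and emails are unscripted, so a caller may well ask why use stopped; one text asks the subject to call and another offers to discuss adherence. Missing entries are themselves reviewed, alongside safety concerns. Stopping PMR is also not the same as stopping the diary: the control arm uses the app with PMR blocked. All of this stands. It limits the conclusion to what is described, and to harms that may be missed. It does not supply a stated question.

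Three stronger readings are tempting and are not supported.

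- A reader might infer that the day-7 contact is too early and should be moved. Four later contacts go to all subjects after home PMR starts. If no contact asks about harm, moving one changes nothing; if they do ask, day 30 can cover the preceding weeks by recall.
- A reader might infer that the between-arm comparison of harm is biased. The documents describe no such comparison.
- A reader might size the loss from the Sample Size paragraph, where diary studies' "follow-up was between 76%–80" percent sits beside over 90% in emergency medicine studies. These are different kinds of outside study, neither gives a rate of loss within this trial, and loss to follow-up does not erase entries already made.

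**Conclusion.** The point holds as a gap in the described collection of harm data. The app diary is the only stated source, safety review draws on it, and no contact is stated to ask about adverse effects or the reason for stopping. Harms in subjects who leave the app may therefore go unrecorded. The documents do not show that such harms will be lost, nor that leaving the app is the usual response to a harm.

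The size cannot be fixed from the documents. At an assumed 5% harm rate, the chance of recording at least one harm falls from 90% to between 43% and 82% if contacts find nothing, and is 88–89% if they find nine in ten of the harms missed by the diary. This rests on equal allocation, on the assumed harm and leaving rates, and on the unseen REDCap forms and main protocol not already asking. For a pilot described as minimal risk, this is a cheap improvement worth making, not a flaw in the primary analysis.

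**What to change.** If the REDCap forms or main protocol already contain these questions, add a cross-reference in the follow-up text. If not:

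- At the five scheduled contacts and the non-completion contacts, ask the same short questions in both arms: any new or worsened problem since the last contact and, if the app or any part of the programme is no longer used, why. Word them neutrally, without naming PMR.
- State that adverse events are counted from the diary and the contacts combined, with an event reported through both counted once.
- Because blinded research assistants collect MSQv2 and MIDAS by telephone, take these items by REDCap self-report or through a team member who does not collect those measures. At the least, place them after MSQv2 and MIDAS; that protects the current contact but not the next one.

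The cost is a few items on existing forms and a protocol modification. The approved texts are a fixed list, so the question would go by call or email unless a message is added. Solicited questions will raise reported events in both arms, and some answers may still reveal the arm before the 3-month outcome.

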For Aim 3, we will use data acquired in Aim 2 to explore predictors of subject response to the PMR intervention. For continuous and categorical outcomes, the effects of the treatment with baseline pain, psychiatric comorbidity, and stress levels on subject outcomes will be examined using linear regression models or generalized linear models, respectively. The multiplicative interaction terms will be created by multiplying the treatment indicator variable with baseline risk factors, and then included in the model. Given the exploratory nature of this aim, we will first examine the baseline factors of interest one-by-one and their significance, and consider multiple factors and their interactions simultaneously. Variable selection and model checking techniques will be considered to derive parsimonious and appropriate models.

Characteristics of the Research Population

Number of Subjects

We had approval for initial beta testing and then for 90 subjects to be recruited. To date (April 2019), we have recruited 22 subjects in the ED and 44 subjects post ED discharge for Aim 1. Now that we have worked to optimize the app and study design, we are requesting that we be able to recruit up to 90 subjects for Aim 2.

This is a pilot study.

Research volunteers in the ED will evaluate which patients are eligible to participate based on the inclusion and exclusion criteria stated below. During the time of covid 19, the research data associate will determine inclusion and exclusion eligibility remotely as described below.

Gender of Subjects

Both genders will be included.

Age of Subjects

18-65

We are excluding patients above the age of 65 because we want the same type of subjects to trial the app as those who will be eligible for the future study with the app.

Racial and Ethnic Origin

No enrollment restrictions.

Inclusion Criteria

age 18–65; Meets migraine criteria based on Information in Study Manual or based on Headache expert opinion if RA has a question and Headache expert, [name], determines that migraine criteria are still met, 4+headache days a month.

Exclusion Criteria

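### The headache-count analysis is an unadjusted test with no rule for choosing it, no named effect estimate and no use of baseline headache frequency; the avoidable power loss is the missing baseline adjustment

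*Combined protocol and SAP*

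**What the plan says.** Under Data Analysis and Data Monitoring Analysis Plan, Sample Size, the headache count is powered twice.

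- By t-test, two-sided at 0.05: 31 subjects per arm are said to "achieve 80% power to detect a difference of 1.42 assuming an SD of 2 in both groups".
- By rank test, from a simulation in which control counts are Poisson with mean 2: the same 31 per arm are said to have ">80% power to detect the difference of 1.4 using a two-sided Mann-Whitney test at significance level 0.05".

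Between the two stands the only sentence on how the count will be analysed: "Potential non-normal distributions will be considered for the count data of the number of headaches and analyzed using nonparametric tests". No diagnostic or threshold decides which test is final. No mean difference, rate ratio, shift or confidence interval is named, and no covariate enters.

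Four other places bear on this.

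- Inclusion Criteria require "4+headache days a month", so every subject is asked about headache frequency before entry.
- Methods & Procedures describes baseline data collection in REDCap without listing the items, and places it after randomization.
- Measurements defines the MIDAS outcome as a change from baseline. The Sample Size text justifies this by less skew and more power.
- Regression appears only for Aim 3, under Study Design. There, effects of treatment with baseline pain, psychiatric comorbidity and stress "will be examined using linear regression models or generalized linear models, respectively".

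**The concern.** Aim 2 asks what the intervention does to headache frequency, and the outcome is sized as a difference in headaches per 30 days. Three things needed to answer that question are not fixed in advance. The test can be chosen after the data are seen. The plan does not commit to an estimate on the scale it was sized on, and a Mann-Whitney test alone does not supply one. Nor does it use how often each subject had headaches before entry, which would ordinarily predict how often they have them afterwards. For a study that calls itself a pilot, an interpretable estimate with its precision is worth more than a p-value.

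**Working it through.** **1. The plan's own figures.** Inputs from the Sample Size text: n = 31 per arm, difference 1.42, SD 2, two-sided 0.05.

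- Noncentrality = (1.42/2) × √(31/2) = 0.71 × 3.937 = 2.795.
- Normal approximation: Φ(2.795 − 1.960) = Φ(0.835) = 79.8%.
- Noncentral t, 60 df: 78.5%. The exact difference for 80% power is 1.45.
- Mann-Whitney, Poisson counts, 20,000 simulated trials: 99.8% for means 2 and 0.6, and 89.6% for 2 and 3.4. The claim of more than 80% holds in both directions.
- Dropout: 62/(1 − 0.30) = 88.6, so 89, consistent with 90 recruited.

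**2. What ranking costs.** In the same Poisson runs the t-test had 99.9% and 91.3%, so the rank test loses 0.1 and 1.7 points. In the simulations of step 4 it loses 1.7 to 4.0 points. The largest loss found was 4.8 points (50.5% against 55.3%), for negative binomial counts with means 4 and 2.6 and dispersion 0.3.

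**3. What the missing baseline costs.** Let ρ be the correlation between baseline and follow-up frequency. The documents do not give it; 0.3 to 0.7 is an assumption. Adjusted residual SD = 2 × √(1 − ρ²), and noncentrality = (1.42/SD) × 3.937. The single degree of freedom spent on the covariate is ignored.

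| ρ | Residual SD | Noncentrality | Power | Difference at 80% power | n per arm for 80% at 1.42 |
|---|---|---|---|---|---|
| 0 (as planned) | 2.000 | 2.80 | 78.5% | 1.45 | 32.1 |
| 0.3 | 1.908 | 2.93 | 82.2% | 1.38 | 29.3 |
| 0.5 | 1.732 | 3.23 | 88.8% | 1.25 | 24.4 |
| 0.7 | 1.428 | 3.91 | 97.1% | 1.03 | 16.9 |

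The gain is about 4 to 19 points. At ρ = 0.2 the SD would fall by only 2% (√0.96 = 0.98), so a weak correlation brings little.

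**4. Illustration with counts.** 1,500 trials per row, 31 per arm, gamma-Poisson counts, entry at a baseline count of 4 or more. Means, shapes and rate ratios are assumptions.

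| Mean before entry rule, gamma shape, rate ratio | Resulting ρ | Mann-Whitney | t-test | Linear ANCOVA | Adjusted quasi-Poisson |
|---|---|---|---|---|---|
| 6, 4, 0.76 | 0.51 | 37% | 41% | 53% | 53% |
| 8, 4, 0.82 | 0.60 | 24% | 27% | 37% | 37% |
| 8, 4, 0.75 | 0.60 | 47% | 51% | 67% | 66% |
| 8, 2, 0.75 | 0.74 | 38% | 39% | 66% | 66% |
| 10, 3, 0.80 | 0.72 | 26% | 28% | 54% | 55% |

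The two adjusted methods agree within a point, so the covariate brings the gain, not the count model. These runs favour adjustment: baseline is a true count, and each subject's underlying rate stays constant apart from treatment.

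**5. Where the gain fades.** In further gamma-Poisson runs, the screening value carried recall error (log-SD 0.5) and each subject's rate was allowed to drift. With drift of log-SD 0.5, adjusted power was 43% against 37% for Mann-Whitney in one setting and 40% against 34% in another. With drift of 0.8 the advantage was gone (23% against 24%). Both error terms are assumptions.

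**The case against.** The best defence is that nothing stated is wrong. The powers reproduce, this is a secondary outcome in a pilot, and under the plan's homogeneous Poisson assumption there is almost no power left to gain. That stands, and it makes this a point about efficiency and interpretability, not an arithmetic error.

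It can also be said that the gain rests on a correlation nobody has supplied. Subjects are recruited around an ED visit, so a recalled frequency may predict the next months poorly. That stands too, and step 5 shows the consequence. In addition, screening asks for headache days while the outcome counts headaches. A covariate need not share the outcome's unit, but the documents show only a threshold, not a recorded number.

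Four stronger readings are tempting and are not supported.

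- A reader might infer that the open choice between t-test and rank test is what loses power. The t-test omits the baseline equally, and ranking itself costs little.
- A reader might infer that a nonparametric analysis cannot use a covariate. That is true of the plain Mann-Whitney test but not of rank ANCOVA, and the plan's wording does not exclude the latter.
- A reader might infer that most of the variance in headache counts is stable difference between subjects. The documents contain no data on this.
- A reader might infer that only a p-value will be reported. The plan does not limit reporting in that way; it simply names no estimate. The document is also an addendum to a main protocol not available here, so a fuller analysis may be described there.

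**Conclusion.** The point holds as a worthwhile, inexpensive improvement. This document states only unadjusted tests for the headache count, gives no rule for choosing between them, commits to no estimate or confidence interval, and leaves baseline frequency unused, although its MIDAS analysis does use the baseline value.

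On the plan's own SD, difference and sample size, adjustment is worth about 4 points of power at a correlation of 0.3, 10 at 0.5 and 19 at 0.7. Below that range the gain is small. The absence of a fixed test and a named estimate does not depend on the correlation.

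**What to change.** At screening, before randomization, record actual headache frequency as a number: ideally headaches per 30 days, the outcome's unit, as well as headache days per month.

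Replace the sentence on non-normal counts with one pre-specified analysis: quasi-Poisson regression of the 30-day headache count on arm and log baseline frequency, with the log of diary days recorded as an offset. State which 30-day window is analysed. The offset matters because the plan itself cites 76% to 80% follow-up in electronic diary studies. Report the rate ratio and the model-based difference in headaches per 30 days, each with a 95% CI. Keep Mann-Whitney as a sensitivity analysis.

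The cost is a few lines of analysis text and one more number at screening; sample size, visits and treatment do not change. The small downside is reliance on a log-link model, which quasi-likelihood errors and the rank-based sensitivity analysis partly cover.
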